### 5.2 Intent-to-Treat Sample

As the primary analysis, all efficacy and safety outcome measures will be analyzed under the intent-to-treat principle (ITT). Under this principle, the evaluable sample includes all subjects who are randomized (regardless of what treatment was actually

received). Each subject will be analyzed according to the treatment group to which they were randomly assigned at the time of randomization.

It should be noted that the role of the ITT population in a non-inferiority trial is not equivalent to that of a traditional superiority trial. The traditional role tends to dilute the treatment effect in favor of no difference between groups; however in the non-inferiority setting this dilution may favor the non-inferiority hypothesis. Therefore the definition of ITT for a non-inferiority trial needs to take into account the impact of missing data on the primary outcome as well as that of non-compliance. For the SVI Trial, non-compliance of the indomethacin alone arm is anticipated to be rare due to the mode of delivery (rectal) and the one-time nature of this intervention. Non-compliance of the combination arm may occur if the endoscopist cannot place the stent however we anticipate this to be minimal. Both of these events are anticipated to be rare (no more than 5%). Missing primary outcome data is also anticipated to be rare with the expectation of minimal loss to follow up due to our brief 30-day follow-up period. Scenarios in which it may occur are if the subject cannot be reached and/or hospital records cannot be obtained. In the event of either of these scenarios, the primary outcome will be imputed (refer below to Handling of Missing Data Section).

### **5.3 Safety Analysis Sample**

All randomized subjects are included in the safety analysis sample.

### **5.4 Per Protocol Sample**

In addition to the defined ITT analysis sample, a per protocol sample is defined as a subset of the ITT sample. This sample will be used for secondary sensitivity analyses of the primary and secondary outcomes. The per protocol sample will include all randomized subjects that do not have the following protocol deviations:

- Eligibility violation
- Treatment crossover
- Missing primary outcome

## **6. RANDOMIZATION**

A web-based central randomization system will be developed by the SDMC and installed on the WebDCU™ SVI study website using a minimal sufficient balance randomization scheme with a 1:1 allocation ratio. Baseline site imbalance will be controlled at the minimal sufficient level so that there will not be serious treatment imbalance within site. The randomization algorithm will be fully detailed and documented in the SVI Randomization Plan and Validation Documents. These documents will be developed prior to the enrollment initiation and stored in a secure location at the SDMC. The documents will be archived with the study database at the end of the trial. Subjects, study coordinators and the adjudicators will all be blind as to which treatment was received. Subjects will not be told of their actual treatment until the Trial completion unless emergency unblinding is required. This information will be accessible in the event of an emergency via an emergency unblinding procedure (see MoP for further details).

## 7. BLINDING

The study is conducted in a single blind manner with double blind outcome assessment. The ERCP team will be unblinded to treatment assignment, however the study subject, clinicians involved in the post-procedure care of the subject, and outcome assessor will be blind to the treatment assignment. Treatment allocation is concealed and subjects will not be told of their actual treatment until the trial completion unless emergency unblinding is required.

The SDMC's unblinded staff will produce two identical sealed envelopes that contain identification of treatment codes. Prior to initiation of the trial, one envelope of (2) is given to the NIDDK Liaison to the DSMB. Another is maintained in a locked file cabinet at the SDMC in its limited access central file room.

The DSMB is partially unblinded for the closed reports (data reported by A and B only). However, if it so wishes, it may be completely unblinded at any time during the trial. If the DSMB wishes to be unblinded on a particular subject only, the NIDDK Liaison to the DSMB should email the request to the unblinded SDMC biostatistician.

## 8. MISSING DATA

Under the ITT principle, all subjects who are randomized are included in the analysis. Although every attempt will be made to prevent incomplete data, a certain amount of missing data is inevitable due to losses to follow-up or withdrawn consents.

[figure not shown]
A thorough analysis of variables, reasons and patterns of missing data will be conducted. Based on the previously conducted indomethacin trial, we anticipate no more than a 5% non-adherence rate. The primary outcome will be determined from hospital records. If these data remain missing despite the extensive efforts mandated in the manual of operations to ensure complete subject follow-up, then the outcome will be imputed.

At the time of each planned analysis (interim and final), the unblinded statistician will report the amount of missing primary outcome data. If there is 5% or less missing primary outcome data, then all missing cases (regardless of treatment arm) will be considered worse case scenario (i.e., having a PEP event). If there is more than 5% missing data, then multiple imputation using SAS PROC MI and MIANALYZE will be used to impute the primary outcome. We chose 5% as our threshold for missing data due to the fact that the performance of the various imputation methods has negligible differences when the amount of missing data is small. In summary, 5 imputed data sets will be generated using PROC MI. The imputation model will include the primary analysis variables (PEP event, treatment) plus age and gender. Each imputed data set will be analyzed according to the specified primary analysis (Section 10.1.2) and MIANALYZE will be used to combine the results from the multiple imputed data sets to obtain a single set of parameter estimates. The multiple imputation method assumes missing at random (MAR) which means that the probability of missing outcome data can depend on the observed values of the individual but not on the missing values of the individual. Although we anticipate minimal missing data, sensitivity analyses will be conducted to assess the impact of any bias due to missing data. The final primary analysis will be re-run using complete case analysis (only those with outcome). If the treatment effect is robust, we expect these sensitivity analyses to yield similar inferences, particularly if the missing data are minimal (~5%). Any discrepancies between the sensitivity analyses and the primary analysis results will be investigated to understand the reason for the discrepancy.

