## 4. NON-INFERIORITY MARGIN AND SAMPLE SIZE DETERMINATION FOR THE PRIMARY OBJECTIVE

### 4.1 Non-inferiority Margin

The non-inferiority margin is set at an absolute margin of 0.05; i.e., indomethacin alone will be considered non-inferior to the combination if it is shown that the upper limit of the two-sided 95% confidence interval of the absolute difference between the two PEP proportions (indomethacin – combination) is less than 5%. The value of this margin is based on a combination of statistical and clinical judgment and was chosen to ensure that the overall PEP proportion of the new treatment (indomethacin alone) demonstrates a clinically unimportant difference from the active comparator arm (the combination of stent and indomethacin) as well as a clinically relevant superiority over a putative placebo (i.e., stent alone). From a statistical perspective, the margin should retain at least 50% of the superiority of the combination of stent and indomethacin (the active control in the trial) when compared to stent alone. Our recent indomethacin RCT revealed that the risk-adjusted proportion of subjects with post-ERCP pancreatitis

in the combination of indomethacin and stent arm was 9.5% and that of stent alone was 15.7%. Unadjusted rates were 9.7% and 16.1%, respectively. Based on these results, the reduction of the combination arm on PEP as compared to stent alone is 6.4%. Therefore, taking a fraction of this value gives a non-inferiority margin ( $\delta$ ) of 3.2% ( $\delta = .5 \times 6.4$ ). This margin is a fraction of the effect of combination compared to stent alone as assessed in the previous trial.

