## 9. EFFICACY ANALYSIS

### 9.1 Primary Outcome Variable Analysis

The analysis of the primary outcome is the difference ( $p_i - p_c$ ) between the two treatment arms in the observed proportion of patients experiencing PEP. This difference will not be adjusted for covariates. However as a secondary analysis of the primary outcome, prognostic variables will be examined as described in detail below. Non-inferiority will be assessed on both the intention-to-treat and per protocol populations (defined above) at the one-sided 2.5% significance level by using the upper bound of the two-sided 95% confidence interval for the difference in PEP event rates. Non-inferiority can be claimed if both analysis populations show non-inferiority (i.e., the two-sided confidence interval is less than 5%).

If (and only if) non-inferiority is claimed, an analysis for superiority will be conducted using a one-sided two-sample test for independent binomial proportions. This test will be conducted at a 0.025 significance level.

Due to a protocol amendment that resulted in a change in the timing of the indomethacin administration (from end of procedure to time of randomization), we have included a sensitivity analysis of the primary outcome. The above analysis will be repeated only including those randomized under the new protocol where indomethacin should be administered at time of randomization. We also will examine the PEP rates in the population that was treated with indomethacin post-

ERCP (initial protocol) as compared to those treated at time of randomization.

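### If more than 5% of outcomes are missing, the ITT limit rests on five imputations with no stated seed and carries chance error of about ±0.3 to ±0.55 points; use at least 50

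*SAP*

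**What the plan says.** SAP section 8 has two branches. At 5% missing or less, every missing outcome in either arm is counted as an event, so nothing is drawn at random. Above that the rule changes: "If there is more than 5% missing data, then multiple imputation using SAS PROC MI and MIANALYZE will be used". The number of draws is set ("5 imputed data sets will be generated using PROC MI") and so is the model: "The imputation model will include the primary analysis variables (PEP event, treatment) plus age and gender". The available text gives no seed and does not say which PROC MI method handles the binary outcome. The sensitivity analysis is a complete-case re-run.

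SAP section 9.1 tests non-inferiority "at the one-sided 2.5% significance level by using the upper bound of the two-sided 95% confidence interval", against the 5-point margin of section 4.1, and adds that "Non-inferiority can be claimed if both analysis populations show non-inferiority". The two populations are ITT and per protocol. Section 5.4 removes subjects with a missing primary outcome from the per protocol sample, so only the ITT result is imputed. Sections 5.2 and 8 expect little missing data.

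**The concern.** Non-inferiority turns on whether one number, the upper limit of the risk difference, is below 5%. With five imputations that number has its own random error, separate from sampling error. Two analysts following the SAP exactly on the same data, with different seeds, can report different limits. If the limit is near 5%, they can report different ITT verdicts. Because ITT is one of two results that must pass, an unlucky seed could block a claim.

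The model is also thin. SAP section 9.3 lists suspected sphincter of Oddi dysfunction, earlier post-ERCP pancreatitis, recurrent pancreatitis, difficult cannulation, sphincterotomy type and inpatient status as variables to examine, and builds a risk score from several of them. None is in the imputation model. Missing at random is conditional on what the model contains, so leaving out known predictors makes that assumption harder to defend.

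**Working it through.** **Inputs from the documents.** Five imputations, the >5% trigger and the model (SAP section 8); 5-point margin and the 12.0% against 9.7% example (section 4.1); 1090 per arm (section 4.2 and protocol summary); 9.7% planning rate (section 4.2); 13% as the high case (section 4.3).

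**Assumptions.** The documents give no missing fraction above 5%, so 5.1% to 10% is examined. They do not state the event rate that prompted the increase to 2,180, so 9.7% to 16% is examined. The 16% is an inference. With section 4.2's 5% non-adherence factor, the effective size is 1090 × 0.95² ≈ 984 per arm. At 16%, SE = √(2 × 0.16 × 0.84 / 984) = 0.01653, and power = Φ(0.05/0.01653 − 1.96) = Φ(1.07) ≈ 86%, close to the 85% target.

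**Reproducing the plan's figures.**
- Power at 650 per arm, 9.7%: SE = √(2 × 0.097 × 0.903 / 650) = 0.01642; Φ(0.05/0.01642 − 1.96) = 86.1%. The SAP says about 85%.
- At 13%: SE = 0.01866; power 76.4%. The SAP says 76%.
- 12.0% against 9.7% at 1090 per arm: 2.3 ± 1.96 × 1.331 = (−0.31%, 4.91%). The SAP says (−0.3%, 4.9%).

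**Method.** Hold the observed data fixed and repeat only the imputation. For each of m data sets, draw each arm's rate from its posterior, fill in the missing outcomes, and compute the difference d and its variance. Pool by Rubin's rules: T = W + (1 + 1/m)B, where W is the mean within-imputation variance and B the between-imputation variance; degrees of freedom (m − 1)[1 + W/((1 + 1/m)B)]²; upper limit = mean d + t√T.

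**Hand check of the noise in mean d.** At 9.7% and 6% missing, each arm has 65 missing and 1025 observed. B ≈ 2 × 65 × 0.0876 × (1 + 65/1025) / 1090² = 1.02 × 10⁻⁵. With m = 5, √(B/5) = 0.143 points; with m = 50, 0.045. The simulated values are 0.142 and 0.045. The limit itself varies a little more, because T and the degrees of freedom also vary.

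**Results for the upper limit, 1090 per arm, seed variation only (percentage points).**

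| Rates | Missing | SD, m=5 | 95% seed range width, m=5 | SD, m=50 |
|---|---|---|---|---|
| 9.7% both | 6% | 0.16 | 0.62 | 0.05 |
| 9.7% both | 10% | 0.23 | 0.90 | 0.07 |
| 13% both | 6% | 0.18 | 0.71 | 0.05 |
| 13% both | 10% | 0.26 | 1.01 | 0.08 |
| 16% both | 6% | 0.20 | 0.78 | 0.06 |
| 16% both | 10% | 0.28 | 1.10 | 0.08 |
| 12.0% vs 9.7% | 6% | 0.17 | 0.66 | 0.05 |

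At 5.1% missing the width is 0.57 (9.7%) to 0.64 (13%). A logistic imputation model on treatment, age and gender, with assumed covariate effects, gives similar widths: 0.63 to 0.68 at 6% and 0.90 to 1.02 at 10%, for rates of 9.7% and 13%.

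**The borderline example with 6% missing.** Observed counts are 123/1025 and 99/1025. The complete-case limit is 2.34 + 1.96 × 1.372 = 5.03%. With m = 5 the central 95% of seeds gives 4.73% to 5.39%, and about 39% of seeds fall below 5%. With m = 50 the range is 4.93% to 5.13%.

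**The case against.** The strongest reply is that this branch may never be used and would rarely matter if it were. The primary outcome comes from hospital records, first contact is within days, and consent covers outside records. When there is truly no difference, the limit is usually well below 5%: letting the trial data vary as well, two seeds gave different verdicts in only 1.0% to 3.0% of trials at 6% missing and 1.7% to 4.8% at 10%, for rates of 9.7% to 16%. With 50 imputations that falls to 0.2% to 1.3%. A result close enough to 5% to be flipped by a seed is marginal anyway, and the planned complete-case re-run would expose it. All of this stands as a limit on how often the problem bites. It is not a reason to keep a pre-specified branch with avoidable noise.

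Three stronger readings are tempting and are not supported.
- A reader might infer that the limit moves by about a point as soon as 5% is exceeded. One point is the full width of the 95% range at about 10% missing. At 5% to 6% missing and rates of 9.7% to 13%, two seeds typically differ by 0.16 to 0.20 points.
- A reader might infer that the imputed ITT result decides the trial. It is necessary, not sufficient: the per protocol result must also pass, so a lucky seed alone cannot produce a claim.
- A reader might infer that omitting the risk factors biases the result. Nothing in the documents shows that these factors predict missingness, still less differently by arm.

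**Conclusion.** The point holds as a contingent weakness of moderate size. If more than 5% of outcomes are missing, five imputations with no stated seed add seed error of about ±0.3 to ±0.4 points to the ITT upper limit at 5% to 6% missing, and about ±0.45 to ±0.55 points at 10%. That is enough to put a borderline ITT result on either side of 5%, and too little to matter when the limit is well clear of it. The figures assume 1090 per arm, equal missingness in both arms and pancreatitis rates of 9.7% to 16%. The thin imputation model is a real but unquantified secondary point.

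**What to change.** In SAP section 8:
- Replace 5 imputations with at least 50, and state the seed in advance. The seed makes the result reproducible; only the larger number reduces the noise. Both are needed, since the borderline example still spans 4.93% to 5.13% with 50.
- Name a logistic imputation method for the binary outcome.
- Add to treatment, age and gender a small set of baseline predictors already collected, for example the section 9.3 risk score or its main components, and inpatient status.
- Do not add separate site terms within arm. With about 20 sites and roughly 106 events per arm at 9.7% (1090 × 0.097), or 174 at 16%, some sites could have few or no events, and the model could fail to fit.

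The cost is a few lines of SAP wording and slightly more computing, with no new data.

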## 9. EFFICACY ANALYSIS

### 9.1 Primary Outcome Variable Analysis

The analysis of the primary outcome is the difference ( $p_i - p_c$ ) between the two treatment arms in the observed proportion of patients experiencing PEP. This difference will not be adjusted for covariates. However as a secondary analysis of the primary outcome, prognostic variables will be examined as described in detail below. Non-inferiority will be assessed on both the intention-to-treat and per protocol populations (defined above) at the one-sided 2.5% significance level by using the upper bound of the two-sided 95% confidence interval for the difference in PEP event rates. Non-inferiority can be claimed if both analysis populations show non-inferiority (i.e., the two-sided confidence interval is less than 5%).

If (and only if) non-inferiority is claimed, an analysis for superiority will be conducted using a one-sided two-sample test for independent binomial proportions. This test will be conducted at a 0.025 significance level.

Due to a protocol amendment that resulted in a change in the timing of the indomethacin administration (from end of procedure to time of randomization), we have included a sensitivity analysis of the primary outcome. The above analysis will be repeated only including those randomized under the new protocol where indomethacin should be administered at time of randomization. We also will examine the PEP rates in the population that was treated with indomethacin post-

ERCP (initial protocol) as compared to those treated at time of randomization.

## 9.2 Interim Analysis Plan

Two interim analyses for futility using conditional power will be conducted when approximately one-third (N~472) of the original sample size (N=1430) and one-half (N~1090) of the revised sample size (N=2180) have been evaluated for the primary outcome and all of the outcomes to be used in the analysis are adjudicated. This timeline can be altered based on the input from the DSMB. The goal of the interim analysis plan is to determine whether to stop the trial early because it is unlikely to show non-inferiority at the final analysis. A conditional power will be calculated to assess the probability of observing non-inferiority at the final analysis conditional on the observed data and assumptions on the PEP event rates for the remainder of the trial. Conditional power will be calculated under two different assumptions: 1) the assumption that the PEP rates in the two treatment arms for the remainder of the trial will be the same as those hypothesized ( $p_C=9.7\%$ ;  $p_I=9.7\%$ ); and, 2) the assumption that the PEP rates observed at the interim analysis will be maintained for the remainder of the trial. The probability of the observed events rates continuing for the remainder of the trial will be provided to the DSMB. Specifically, we will calculate the probability of observing the results at the interim look (or more extreme values) assuming that the hypothesized event rates are true. If these probabilities are low, then it may be more appropriate to use the conditional power results under the assumption of the observed rates. Conditional power will be calculated for three analysis samples: the ITT samples (see section 5.2), the per protocol sample (see section 5.4), and the ITT time sample. The ITT time sample includes subjects randomized under protocol version 3 or later, where indomethacin should be administered at the time of randomization.

A formal, non-binding stopping guideline is provided to the DSMB in order to preserve the type II error rate (claiming inferiority when in fact non-inferiority is present). If the conditional power falls below 20% then the DSMB may consider recommending to stop the trial due to futility. A formal stopping rule for overwhelming ‘non-inferiority’ is not provided as the study team would only like to stop the study early for overwhelming ‘superiority’. If the conditional power (as defined above) under either assumption is 100% at either interim assessment then the statistical team will conduct a one-sided binomial test of two independent proportions to determine if statistical significance for superiority is met. Superiority is based on this one-sided test and defined as the event proportion being statistically lower ( $p<0.025$ ) in the RI arm as compared to the combination arm. If met, the DSMB may consider recommending to stop the trial due to overwhelming efficacy (superiority). A simulation study was conducted to examine the operating characteristics based on various conditional power thresholds using a control event proportion of 9.7% and 13% at the interim looks. These results guided our decision to only test for superiority if the conditional power is 100%.

First Interim Analysis (n=238 per arm)

Control arm PEP rate ≈ 9.7% (n=23)			Control arm PEP rate ≈ 13% (n=31)		
Subjects with PEP in Experimental Arm	Conditional Power	One-Sided Chi-Sq p-value	Subjects with PEP in Experimental Arm	Conditional Power	One-Sided Chi-Sq p-value

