13.4 Interim Analysis

Two interim analyses for futility using conditional power will be conducted when approximately one-third (N~472) of the original sample size and one-half (N~1090) of the revised sample size (N=2180) have been evaluated for the primary outcome and all of the outcomes to be used in the analysis are adjudicated. The goal of the interim analysis plan is to determine whether to stop the trial early because it is unlikely to show non-inferiority at the final analysis. A conditional power will be calculated to assess the probability of observing non-inferiority at the final analysis conditional on the observed data and assumptions on the PEP event rates for the remainder of the trial. Conditional power will be calculated under two different assumptions: 1) the assumption that the PEP rates in the two treatment arms for the remainder of the trial will be the same as those hypothesized (pC=9.7%; pI=9.7%); and, 2) the assumption that the PEP rates observed at the interim analysis will be maintained for the remainder of the trial. See the Statistical Analysis Plan for more details.

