## 2. SYNOPSIS OF THE STUDY

The purpose of the SVI study is to determine whether or not rectal indomethacin has no important loss of efficacy as compared to the combination of rectal indomethacin and prophylactic pancreatic stent placement in patients undergoing high-risk ERCP who require pancreatic stent placement (PSP) for the sole purpose of pancreatitis prevention. The primary efficacy endpoint is defined as post-ERCP pancreatitis defined per consensus (Atlanta) criteria. Another way of stating the trial's purpose is that the proportion of subjects with post-ERCP pancreatitis on rectal indomethacin alone is not more than that of the combination of rectal indomethacin and prophylactic PSP by more than a pre-specified absolute amount (i.e., the non-inferiority margin).

The recently conducted trial by the SVI PI showed that indomethacin in addition to PSP protects against post-ERCP pancreatitis as compared to pancreatic stent alone. Because the combination treatment is already proven to be highly efficacious (low post-ERCP pancreatitis rate), the superiority of indomethacin alone in terms of efficacy is not of main interest. Rather, indomethacin alone offers the appealing characteristics of lower costs and potential of avoiding the phenomenon of attempted but failed PSP as well as the complications associated with placing a stent; therefore, the research goal is to determine if the post-ERCP pancreatitis rate of indomethacin alone is no more than some clinically acceptable amount from the rate for the combination treatment. To answer this question, a blinded, two-armed non-inferiority trial is designed. In summary, eligible subjects will be randomized to either the combination treatment or indomethacin alone. Subjects will be randomized during the ERCP procedure after eligibility is confirmed, and receive indomethacin at the time of randomization. The primary efficacy endpoint of post-ERCP pancreatitis within 2 days from randomization will be assessed by an independent adjudication panel. The duration of enrollment into the trial is anticipated to be four years. The subject follow-up period is 30 days from randomization.

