The sample size was increased to a maximum of 2,180 in order to attain 85% power. This increase was due to an observed higher event rate at the time of the first interim analysis. The DSMB recommendation was based on the review of the blinded sample size re-estimation and the conditional power analysis presented at the time of the first interim analysis in September 2017.

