**Second Interim Analysis (n=545 per arm)**

Control arm PEP rate ≈ 9.7% (n=53)				
Subjects with PEP in Experimental Arm		Conditional Power		One-Sided Chi-Sq p-value
N	Current PEP Rate	Assuming current PEP rate	Assuming 9.7% PEP rate	
35	6.42%	100%	100%	0.0227*
36	6.61%	100%	100%	0.0300
40	7.34%	100%	100%	0.0793
50	9.17%	100%	100%	0.3780
54	9.91%	100%	100%	0.4595
55	10.09%	99%	99%	0.4197
60	11.01%	90%	98%	0.2434
70	12.84%	21%	83%	0.0518
71	13.03%	15%**	81%	0.0430
80	14.68%	0%**	46%	0.0062
87	15.96%	0%**	20%	0.0010
88	16.15%	0%**	17%**	0.0008

\*Stop for superiority

Control arm PEP rate ≈ 13% (n=71)				
Subjects with PEP in Experimental Arm		Conditional Power		One-Sided Chi-Sq p-value
N	Current PEP Rate	Assuming current PEP rate	Assuming 9.7% PEP rate	
50	9.17%	100%	100%	0.0214*
51	9.36%	100%	100%	0.0273
60	11.01%	100%	100%	0.1528
68	12.48%	100%	100%	0.3927
69	12.66%	99%	100%	0.4282
70	12.84%	99%	100%	0.464
71	13.03%	99%	100%	0.5
72	13.21%	98%	99%	0.4643
80	14.68%	66%	95%	0.215
87	15.96%	20%	82%	0.0843
88	16.15%	15%**	78%	0.0723
90	16.51%	9%**	72%	0.0524
100	18.35%	0%**	31%	0.0079
103	18.90%	0%**	21%	0.0041
104	19.08%	0%**	18%**	0.0032

\*\*Stop for futility

The SDMC will be responsible for conducting these analyses and compiling the reports for the DSMB. Since several factors need to be taken into consideration before stopping a study, safety and study progress also will be taken into consideration by the DSMB and NIDDK in the decision to stop the study if the futility boundary is crossed.

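### Superiority can be declared at an interim and again at the end, each at an unadjusted one-sided 0.025; over the looks still to come the false-superiority risk is up to about 3.4%, and over all three looks up to 5.8%

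*SAP*

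**What the plan says.** SAP 9.2 sets two interim looks, at about 472 and about 1090 subjects, with a final total of 2180. Its tables use 238 and 545 per arm. The main purpose is futility, but the section adds an efficacy route. If conditional power for non-inferiority "under either assumption is 100% at either interim assessment then the statistical team will conduct a one-sided binomial test of two independent proportions". Superiority means one-sided p<0.025 for a lower PEP proportion on indomethacin alone. If that is met, "the DSMB may consider recommending to stop the trial due to overwhelming efficacy (superiority". The second-interim table marks 35 v 53 events with "Stop for superiority".

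SAP 9.1 tests superiority at the end once non-inferiority has been claimed: "This test will be conducted at a 0.025 significance level".

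Three other places bear on the point:

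- SAP 4.2 refers to the "conditional power analysis presented at the time of the first interim analysis in September 2017", so the first look is past.
- SAP 2 says that "the superiority of indomethacin alone in terms of efficacy is not of main interest".
- Protocol 13.4 describes the looks only as futility: "Two interim analyses for futility using conditional power will be conducted". It does not mention a superiority test.

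Neither document gives a spending function, an adjusted interim level or a reduced final level for superiority. SAP 9.2 mentions a simulation behind the conditional-power threshold but reports no false-superiority rate from it. The statement in SAP 4.3 about preserving error rates covers only sample size re-estimation combined with futility.

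**The concern.** Testing one hypothesis at up to three looks, each at 0.025, does not hold 2.5% overall. The only extra hurdle at an interim is conditional power for non-inferiority against a 5-point margin. A result that significantly favours indomethacin alone is already far inside that margin, so the hurdle screens out nothing.

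Two things are at stake. A superiority claim would carry more than its stated error. A stop described as resting on overwhelming evidence could also come from an ordinary p just under 0.025 in half the planned patients. At the starred row of 35 v 53 of 545, the difference is -3.3 points with a 95% interval of -6.5 to -0.07, which is borderline.

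**Working it through.** **Inputs.** Interim level 0.025, one-sided (SAP 9.2). Final level 0.025, one-sided (SAP 9.1). Per-arm sizes 238 and 545 (tables in SAP 9.2) and 1090 (half of 2180, SAP 4.2). Event rates 9.7% and 13% (SAP 9.2); 16.5% is an added assumption to test sensitivity.

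**1. The plan's own p-values.** Pooled z = (p_C - p_I) / sqrt[2·p̄(1 - p̄)/n], without continuity correction:

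| Events, indomethacin v combination | n per arm | z | One-sided p | SAP table |
|---|---|---|---|---|
| 11 v 23 | 238 | 2.136 | 0.0164 | 0.0164 |
| 17 v 31 | 238 | 2.131 | 0.0165 | 0.0165 |
| 35 v 53 | 545 | 2.001 | 0.0227 | 0.0227 |
| 50 v 71 | 545 | 2.025 | 0.0214 | 0.0214 |

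All four agree, so the SAP's superiority test is the uncorrected chi-square.

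**2. The conditional-power condition.** All four starred rows show 100% under both assumptions. In simulation of the ITT sample, taking the higher of the two assumptions (target 715 per arm at the first look, 1090 at the second), the lowest conditional power at any p<0.025 crossing was 99.9997%. No crossing is filtered out.

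**3. False superiority with equal true rates.** The z statistics at the three looks are multivariate normal with correlation sqrt(n_j/n_k):

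- sqrt(238/545) = 0.661
- sqrt(238/1090) = 0.467
- sqrt(545/1090) = 0.707

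The risk is 1 - P(all z < 1.96):

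- all three looks: 5.78%
- the two interims: 4.26%
- second interim plus final: 4.16%
- second interim or final, given no crossing at the first: (0.0578 - 0.025)/0.975 = 3.37%

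Binomial simulation (2,000,000 trials each at 9.7%, 13% and 16.5%, final superiority only after ITT non-inferiority) gives 5.82-5.84%, 4.15-4.18% for the last two looks, and 3.36-3.38% for those two given no first-look crossing.

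**4. Effect on the non-inferiority conclusion.** With a true difference of +5 points, an interim superiority crossing occurs in 0.016% to 0.042% of trials. Total false endorsement of indomethacin alone moves from 2.53-2.56% to 2.54-2.57%.

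**5. Remedy.** O'Brien-Fleming-type spending at 50% information gives 2·[1 - Φ(2.2414/√0.5)] = 0.00153. Levels of 0.0015 at the second interim and 0.0245 at the end give:

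| Risk | Now | After |
|---|---|---|
| Second interim + final, ignoring the first look | 4.16% | 2.50% |
| The same, given no first-look crossing | 3.37% | 2.11% |
| All three looks, first look left at 0.025 | 5.78% | 4.56% |

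At the second interim with 53 control events, 27 indomethacin events would cross (p=0.0013) and 28 would not (p=0.0019). With 71 control events, 41 would cross (p=0.0014) and 42 would not (p=0.0020).

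**The case against.** The strongest reply is that the effect is small and narrow.

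- **Ceilings.** The DSMB may only consider a recommendation, and protocol 13.5 makes it consultative to NIDDK. This stands: every figure assumes that each crossing is acted on.
- **The past look.** The 5.8% includes a look that cannot be undone, so 3.4% is the figure to act on. This also stands. That no crossing occurred is inferred from the trial having continued; the documents do not report it.
- **Choice of test.** With Fisher's exact test the figures fall to 4.6-4.8% overall and 2.9-3.0% for the remaining looks given no crossing. That is still above 2.5%, and the SAP's tables use chi-square.
- **Consequence.** When the true rates are equal, non-inferiority is true. A false crossing therefore overstates the claim but does not endorse a worse strategy. This is fair, and it limits the weight of the point.
- **Calibration.** The proposed levels are set to the two remaining looks taken alone. They are stricter than needed given no first-look crossing, and they do not bring the three-look total to 2.5%. They are also not the only choice: 0.0026 and 0.0240 also give 2.50%.

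None of this supplies the missing adjustment. The plan names 0.025 for superiority and does not hold it.

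**Conclusion.** The concern holds and should be fixed. The superiority error is up to 5.8% over three looks and up to 3.4% over the two that remain, given no crossing at the first, against a nominal 2.5%. These figures assume equal true rates, the chi-square test of the SAP's tables, looks at 238, 545 and 1090 per arm, every crossing acted on, and the rule having applied at the first interim.

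SAP 9.2 computes conditional power in three samples (ITT, per protocol and ITT time) and does not say which must reach 100% or which is used for the superiority test. Only ITT was modelled, and testing in more than one sample would add to the risk. The primary non-inferiority conclusion is essentially unaffected.

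**What to change.** 1. In SAP 9.2, for the second interim, replace p<0.025 with about p<0.0015. Name the spending function, and have both levels recomputed at the actual information fraction if the DSMB moves the look, as SAP 9.2 allows.
2. In SAP 9.1, set the final superiority level to about 0.0245.
3. In SAP 9.2, state that the 100% conditional-power condition is not error control, and name the sample used for the superiority test.
4. Re-mark the second-interim tables. The superiority stops move from 35 to 27 events (53 control events) and from 50 to 41 (71 control events).
5. In protocol 13.4, disclose the superiority look.

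The first look cannot be changed and should be acknowledged when any superiority result is reported.

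**Cost.** A few lines of text and the approvals in protocol 14.2.2 (Executive Committee and NIDDK, with DSMB review if the change is substantive). The levels should be set by people who have not seen the interim results by arm. No patients are added and the non-inferiority test is unchanged. At assumed true rates of 13% v 10%, the chance of showing superiority at the second interim or the end falls from 62.9% to 59.1%, against 59.3% for a single final test at 0.025. Stopping early for superiority becomes harder.
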